3.2 Secondary

- Tolerability and safety of troriluzole will be measured by the frequency and severity of adverse events and discontinuations of adverse events.
- Patient Global Impression of Change (PGI-C);

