- Admission encountered for another life circumstance that carries no bearing on health and requires no medical intervention (i.e., lack of housing, care-giver respite, family circumstances).

Disability/incapacitating: An AE is incapacitating or disabling if the experience results in a substantial and/or permanent disruption of the subject's ability to carry out normal life functions.

Classification of Adverse Events

The severity of all AEs must be recorded in the eCRF and on the SAE Form, if applicable. The severity or intensity of an AE refers to the extent to which it affects the subject's daily activities. The severity of events should be graded as mild, moderate or severe. Refer to the BHV4157-201 SAE Reporting and Management Plan for definitions of each grading criteria.

The Investigator's assessment of an AEs relationship to study drug is part of the documentation process but is not a factor in determining what is or is not reported in the study. If there is any doubt as to whether a clinical observation is an AE, the event should be reported. The relationship or association of the study drug in causing or contributing to the AE will be characterized as either not related, unlikely related, possibly related, or related. Refer to the BHV4157-201 SAE Reporting and Management Plan for definitions of each criteria.

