11 ADVERSE EVENTS

Treatment-related AEs are defined as any AE considered unlikely related, possibly related, or related. This is an update to Section 4.8.2 of the SAP (v2.0) where AEs related to treatment were only inclusive of those considered definitely related, probably related, or possibly related. This has been updated to match the options in the Case Report Form (CRF).

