2.4. Efficacy, Safety, and Other Variables

2.4.1. Efficacy Variables

Primary Endpoint

• Change from baseline to Week 8 in SARA total score

Secondary Endpoints

- Frequency and severity of adverse events (AEs) and discontinuation due to AEs
- Patient impression of benefit via use of PGI-C at Week 8

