4.8.2. Adverse Events

Adverse eventss will be coded using MedDRA and displayed in tables and listings by system organ class (SOC) and preferred term (PT).

Analyses of AEs will be performed for those events that are considered treatment-emergent, where treatment-emergent is defined as any AE that developed, worsened, or became serious after first dose of test treatment.

Adverse events are summarized by subject incidence rates; therefore, in any tabulation, a subject contributes only once to the count for a given AE (SOC or PT).

The number and percentage of subjects with the following on-treatment AEs will be summarized by treatment group and overall for the Randomization and Extension Phases, separately.

- Treatment-emergent AEs,
- AEs related to treatment (definitely, probably, or possibly),
- SAEs,
- AEs with Grade 2 or greater severity,
- AEs leading to discontinuation, and
- Standardized MedDRA query (SMQ) of interstitial lung disease, including eosinophilic pneumonia

On-treatment AEs are AEs with a start date prior to 30 days after the last dose of study drug. For the Randomization Phase, treatment-emergent AEs will be assessed from the date of randomization until: 1) the first day of the Extension Phase or 2) if the subject did not continue into the Extension Phase, 30 days after the last dose of study drug. For the Extension Phase, treatment-emergent AEs will be assessed from the first day of the Extension Phase until 30 days after the last dose of study drug.

In the above tabulations, each subject will contribute only once (i.e., the most related occurrence or the most severe occurrence) to each of the incidence rates in the descriptive analysis, regardless of the number of episodes. No formal hypothesis-testing analysis of AEs incidence rates will be performed.

All AEs occurring pre-treatment, during the Randomization phase, during the Extension phase, and throughout the entire study will be listed. Additional listings will be provided for the Randomization and Extension Phases, including deaths, SAEs, and AEs leading to withdrawal of study drug.

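### The only visible severity row in the SAP's adverse event tables uses an undefined grade and, on its natural reading, pools moderate with severe events, so no visible planned by-arm table reports severe events separately

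*SAP*

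**What the plan says.** Protocol section 3.2 makes severity part of a secondary endpoint: "Tolerability and safety of troriluzole will be measured by the frequency and severity of adverse events", together with discontinuations. SAP section 2.4.1 repeats it as "Frequency and severity of adverse events (AEs) and discontinuation due to AEs".

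On data collection, the classification text in Protocol section 8.1.2 states: "The severity of all AEs must be recorded in the eCRF and on the SAE Form, if applicable". On the scale it states: "The severity of events should be graded as mild, moderate or severe". The same section describes each level in words and refers to a separate SAE Reporting and Management Plan for the grading definitions. That plan and the CRF are not among the documents.

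On analysis, SAP section 4.8.2 lists six adverse event summaries that "will be summarized by treatment group and overall for the Randomization and Extension Phases, separately": treatment-emergent, related to treatment, serious, a severity row, leading to discontinuation, and an interstitial lung disease query. The severity row reads "AEs with Grade 2 or greater severity". A later sentence counts each subject once, at the most related or most severe occurrence.

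Section 11 of the SAP addendum changes which relatedness categories count as treatment-related, so that they agree with the CRF. It does not mention severity. Addendum section 10 announces updates to the analyses in the SAP, but its content is not shown.

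**The concern.** There are two separate defects.

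The first is the label. The row uses a numbered grade, the protocol collects three verbal levels, and nothing visible links them. The relatedness row in the same list also disagreed with the collected categories, and the addendum corrected it for that reason. The severity row looks like the same kind of oversight.

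The second is the pooling, and it matters more. Stating that Grade 2 means moderate would settle the label and still leave one count of moderate or severe events. Moderate events may well outnumber severe ones. An imbalance in severe events could then be diluted, or offset by an opposite imbalance in moderate events. Protocol section 10.1 provides for no data monitoring committee, so these by-arm tables carry much of the randomized tolerability comparison.

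**Working it through.** The plan gives no figure for adverse event severity, so there is none to reproduce on this point. Its one design calculation reproduces: Φ(1.24 / (2.01 × √(2/56)) − 1.96) = Φ(3.264 − 1.96) = 0.904 by the normal approximation, and 0.899 by the noncentral t with 110 degrees of freedom, against a stated 90% or so. It is used here only for scale: about 120 subjects randomized 1:1 is 60 per arm.

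**Step 1: is there a by-arm count of severe events elsewhere?**

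- Serious events (SAP 4.8.2): seriousness has its own criteria in Protocol 8.1.1. An event that interrupts daily activities is severe under 8.1.2 and need not be serious.
- Discontinuations (SAP 4.8.2): these miss severe events handled by the dosing changes that Protocol 7.2.3 allows.
- Displays by system organ class and preferred term: no severity split is named.
- By-subject listings: complete, but they give no rates by arm.
- The once-per-subject rule: it sets how a subject is counted within the listed summaries and names no severity table.
- Protocol 9.1: a general promise of descriptive statistics for all outcome measures, with no table specified.
- Protocol 9.3.3: counts and percentages of treatment-emergent events, with no severity breakdown.

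None of these is a severe-only count by arm.

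**Step 2: what does the pooled row reveal?** Take Grade 2 as moderate. For each arm, let m be subjects whose worst event is moderate and s be subjects with any severe event. The row reports (m + s)/60. A value of 15/60 is compatible with any s from 0 to 15, that is, from 0% to 25%. The row alone does not identify s.

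**Step 3: illustration.** All counts below are assumed; none comes from the documents. Sixty subjects per arm.

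| Case | Placebo m + s | Troriluzole m + s | Pooled row, placebo vs troriluzole | Severe, placebo vs troriluzole | Fisher p, severe |
|---|---|---|---|---|---|
| A | 20 + 2 | 18 + 6 | 36.7% vs 40.0% | 3.3% vs 10.0% | 0.27 |
| B | 15 + 0 | 9 + 6 | 25% vs 25% | 0% vs 10.0% | 0.027 |
| C | 14 + 1 | 8 + 7 | 25% vs 25% | 1.7% vs 11.7% | 0.061 |
| D | 14 + 1 | 12 + 3 | 25% vs 25% | 1.7% vs 5.0% | 0.62 |

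In case A the pooled ratio is 40.0/36.7 = 1.09 and the severe ratio is 6/2 = 3.0. In cases B to D the pooled row shows no difference at all. The p-values only indicate how much evidence such counts would carry; the plan tests no adverse event rates.

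**Step 4: dependence on the mapping.** The result needs Grade 2 to mean moderate. If the levels were coded from zero, so that 2 meant severe, the row would already be a severe-only count. Nothing visible suggests that coding, but without the CRF it cannot be excluded.

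**The case against.** A reader might infer that severe events are never counted by arm in this trial and that the addendum left the row as it was. The documents do not support either statement. Addendum section 10 exists to update the SAP analyses and its content is not shown; text that has been removed cannot be treated as absent from the plan. What can be said is that the visible section 11 does not change the row. Since section 11 is the adverse event section, this limits the claim but does not remove it.

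A reader might also infer that the row cannot be produced, or that severe events are lost because the scale is wrong. Neither follows. Three ordered levels are recorded, so the row can be produced once a mapping is stated. The loss comes from pooling.

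The once-per-subject rule is the best counter-evidence. A yes/no row needs no rule about the most severe occurrence, so the sentence hints that someone had a tabulation across severity levels in mind. It may equally be standard wording, and it specifies no table. The general sentence in Protocol 9.1 is weaker still.

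On consequences, the other summaries would catch many clinically important severe events, and the listings of a trial of about 120 subjects can be read in full. That stands: it reduces the risk of missing a signal but does not supply by-arm rates. The illustration uses invented rates, and case A rests on 6 versus 2 subjects. It shows that pooling can mask a difference, not that it would do so here.

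**Conclusion.** The concern holds in a limited form. In the visible plan, the severity part of a secondary endpoint comes down to one row on an undefined grade. On the natural reading that row cannot separate severe from moderate events, and no other visible by-arm table does so.

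This rests on three assumptions: Grade 2 means moderate; the unseen section 10 of the addendum does not already add a severity table; and the CRF follows the three levels in Protocol 8.1.2.

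The size cannot be fixed from the documents. In the assumed cases, the masked gap in severe events runs from 3.3 percentage points (D: 5.0 − 1.7) to 10 points (B: 10.0 − 0; C: 11.7 − 1.7).

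It would be wrong to conclude that a confirmatory result is at risk. SAP 4.2.5 tests only SARA and then PGI-C, and SAP 4.8.2 rules out formal testing of adverse event rates. This is an inexpensive improvement to descriptive safety reporting that should be made.

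**What to change.** First check the full text of addendum section 10. If it does not already deal with this, replace the severity row in SAP 4.8.2, and record the change in addendum section 11, along these lines:

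*Subjects with treatment-emergent adverse events by maximum recorded severity (mild, moderate, severe), with the number and percentage of subjects with any severe event, by treatment group and overall, for the Randomization and Extension Phases separately.*

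The existing rule of counting each subject at the most severe occurrence applies unchanged. If a pooled row is kept as well, call it moderate or severe instead of using a grade number.

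The cost is one line of text and one table shell. Severity is already required in the eCRF for every event, so no new data are needed. The table is descriptive and its categories are set by the protocol, so it raises no multiplicity question.

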4.8.3. Laboratory Data

Clinical laboratory evaluations include:

- Hematology: hemoglobin, hematocrit, platelets, complete blood count with differential and absolute neutrophil count
- Serum Chemistry: sodium, potassium, chloride, calcium, alanine aminotransferase (ALT), aspartate aminotransferase (AST), lactate dehydrogenase (LDH), alkaline phosphatase (ALP), gamma-glutamyl transferase (GGT), phosphorous, bicarbonate, creatine phosphokinase (CPK), total protein, albumin, total bilirubin (if greater than 2 mg/dl bilirubin will be fractionated), glucose, creatinine, blood urine nitrogen (BUN), uric acid, and pregnancy testing (for women of child-bearing potential). Additionally at screening, total cholesterol, low-density lipoprotein (LDL), high-density lipoprotein (HDL), triglycerides, folate, hemoglobin A1c (HbA1C), P-Amylase, Lipase, thyroid-stimulation hormone (TSH), and T4
- Urinalysis: pH, specific gravity, protein, ketones, glucose, blood, and microscopic exam (completed only if any part of the urinalysis is not negative)
- Additional tests: human immunodeficiency virus (HIV), hepatitis B surface antigen (HBsAg), and hepatitis C virus (HCV) antibody at screening

Clinical laboratory values will be expressed using conventional units. In the event of repeat values within the same analysis visit, the measurement closest to the target day for the analysis visit interval will be used.

On-treatment laboratory abnormalities are those with an assessment date after the date/time of first dose of study drug and within 30 days after the last dose of study drug. For the Randomization Phase, treatment-emergent laboratory abnormalities will be assessed from the date of randomization until: 1) the first day of the Extension Phase or 2) if the subject did not continue into the Extension Phase, 30 days after the last dose of study drug. For the Extension Phase, treatment-emergent lab abnormalities will be assessed from the first day of the Extension Phase, treatment-emergent lab abnormalities will be assessed from the first day of the Extension Phase until 30 days after the last dose of study drug.

The observed value and change from baseline will be summarized for each continuous laboratory parameter for the Randomization and Extension Phases, separately. In addition, the shift from baseline for laboratory abnormalities (low, normal, high) will be tabulated for the Randomization and Extension Phases, separately.

For the liver function tests, AST and ALT, the shift from baseline will be presented by visit and to the maximum observed abnormality for the Randomization and Extension Phases, separately. Additionally for ALT, the shift from baseline to the maximum observed treatment-emergent abnormality, regardless of phase, will be presented for subjects treated with BHV4157 only. The following categories will be used to summarize the shift from baseline based on the upper limit of normal (ULN) range:

- Normal
- >ULN to \leq 3x ULN
- >3x ULN to $\le 5x$ ULN
- >5x ULN

All laboratory data will be presented in data listings. Additional listings will be presented for all abnormal laboratory values for the Randomization and Extension Phases, separately. Subjects with a maximum value of ALT or AST >3x ULN and a maximum total bilirubin value >2x

ULN observed at any point during the entire study will also be presented in a listing. Note that these abnormalities do not need to occur on concurrent visits.

4.8.4. Physical Examinations

For each body system, the shift from baseline will be summarized as the number and percentage of subjects with each result (normal, abnormal, or physical examination not done) by visit for the Randomization and Extension Phases, separately.

4.8.5. Vital Signs and Physical Measurements

The observed value and change from baseline in vital signs will be summarized at each visit for the Randomization and Extension Phases, separately.

4.8.6. Electrocardiogram

The shift from baseline in ECG parameters will be summarized as the number and percentage of subjects with normal, abnormal, and clinically significant abnormal results by visit for the Randomization and Extension Phases, separately. Descriptive statistics for ECG interval data (e.g., QRS, PR, QT, QTcF), and ventricular heart rate will also be reported by visit for the Randomization and Extension Phases, separately.

4.8.7. Neurological Assessment

For each neurological site, the shift from baseline will be summarized as the number and percentage of subjects with each result (normal, abnormal, or neurological assessment not done) by visit for the Randomization and Extension Phases, separately.

4.8.8. Concomitant Medications

Concomitant medications will be coded using the WHO-DD. Results will be tabulated by Anatomic Therapeutic Class (ATC) and PT during the Randomization and Extension Phases, separately.

4.8.9. Sheehan-Suicidality Tracking Scale (S-STS)

The S-STS is a prospective, self-reported rating scale that contains 16 questions to track both treatment-emergent suicidal ideation and behaviors. In the event the subject is unavailable, the S-STS clinician-administered rating scale will be completed that contains 6 yes/no questions.

Self-reported S-STS scores are calculated as follows:

- Ideation subscale score: Sum of scores (0-4) for Questions 2-11
- Behavior subscale score: Sum of scores (0 4) for Questions 1a, (highest of 12 or any row of 16), (highest of 14 or any row of 15), 17, and 20
- Total score: Sum of the ideation and behavior subscale scores

The self-reported S-STS ideation subscale, behavior subscale, and total score will be summarized as the change from baseline (i.e., <-1, -1, no change, 1, >1) at each visit in the Randomization and Extension phases, presented separately.

Confidential 06Sep2017

5. **REFERENCES**
